8.4 Pharmacodynamic Assessments

A CSF sample will be collected at the time points noted in the Schedule of Assessments to determine the change from baseline in concentration of mHTT protein. All CSF samples should be collected using an atraumatic needle. A plasma sample will be collected at the time points noted in the Schedule of Assessments ([Section 4.2](#)) to determine the change from baseline in concentration of NfL. In addition, the change from baseline in other measures of PD activity in CSF, plasma, or PBMCs will be assessed (e.g., tHTT, wtHTT, and NfL). Additional exploratory biomarkers (e.g., total tau) may also be evaluated.

The study may utilize the method described by Wild et al³⁶ or an alternative method to determine levels of mHTT protein.

Samples will only be used by the Sponsor and/or a contracted vendor for research related to the development of treatments for HD and stored for a maximum of 10 years. All biological material will be stored and secured in a way that ensures that unauthorized access is prohibited and the samples are not lost, deteriorated, or destroyed accidentally or illegally. Detailed instructions on sample collection, storage, processing, and shipping will be provided in the Laboratory Manual.

8.5 Immunogenicity Assessments

Serum samples will be collected at the times noted on the Schedule of Assessments and analyzed at a central laboratory for measurement of anti-drug antibodies to WVE-003.

All biological material will be stored and secured in a way that ensures that unauthorized access is prohibited and the samples are not lost, deteriorated, or destroyed accidentally or illegally. Detailed instructions for sample collection, storage, processing, and shipping will be provided in the Laboratory Manual.

8.6 Magnetic Resonance Imaging

A 3-Tesla MRI of the whole brain (without contrast) will be performed at the time points noted on the Schedule of Assessments. Sedation is permitted during the MRI.

The MRI will be assessed for safety purposes, in addition to exploratory structural assessments. Exploratory assessments will include, but are not limited to, volumetric assessments. Changes in MRIs of the brain will be characterized in patients receiving WVE-003.

The MRI will be performed by an appropriately trained individual. Detailed instructions on how the MRI will be performed and transferred to the central reader are provided in the Imaging Manual. The scans will be evaluated by a central reader.

8.7 Clinical Effects

8.7.1 *Unified Huntington's Disease Rating Scale*

The UHDRS is a research tool developed by the Huntington Study Group to provide a uniform assessment of the clinical features and course of HD³⁷. The scale consists of 6 subtests, including motor assessment, cognitive assessment, behavioral assessment, an independence scale, functional assessment, and TFC, and is provided in the Study Manual. All subtests of the UHDRS should be performed except the behavioral assessment, as the PBA-s ([Section 8.7.2](#)) collects similar behavioral information.

The motor assessment evaluates motor features of HD with standardized ratings of oculomotor function, dysarthria, chorea, dystonia, gait, and postural stability. The total motor impairment score is the sum of all the individual motor ratings, with higher scores indicating more severe motor impairment than lower scores.

The cognitive assessment consists of a lexical verbal fluency test, SDMT, and the Stroop Interference test. The Stroop Test results are reported as the raw number of correct answers given in a 45-second period. Results for the other tests are reported as the raw number of correct responses. Higher scores indicate better cognitive performance.

The independence scale is used to follow disease progression in functional disability. The scale is rated from 100 (no special care needed) to 010 (tube-fed, total bed care).

The functional assessment checklist is a 25-question assessment that screens for capacity to complete the tasks mentioned in the assessment alone. The questions are asked in the presence of a family or friend to get the clinician's best judgment based on both responses. A response of "yes" is given a score of 1. A high score indicates better functioning.

The TFC is a brief interview involving the patient and a close family member or friend familiar with the patient's functioning. The measure has 5 items and addresses basic activities of living: occupation, handling finances, domestic responsibilities, activities of daily living (e.g., eating, dressing, bathing), and level of care.

8.7.2 Short Problem Behaviors Assessment

The PBA-s is a shorter version of the Problem Behaviors Assessment for HD (PBA-HD), a semi-structured interview designed to elicit information about behavioral symptoms relevant to HD. The shorter version was developed by the Behavioral Phenotype Working Group of the European Huntington's Disease Network (EHDN)³⁸.

The PBA-s contains 11 items, each measuring a different behavioral problem that is rated for both severity and frequency on a 5-point scale. Severity and frequency ratings are multiplied to provide an overall score for each symptom. The PBA-s is provided in the Study Manual.

Interviews are conducted with the patient. The final rating is determined by assessing all available information, including the interviewer's own observations of the patient's behavior. A study partner may also be interviewed as part of the PBA-s for this study if they are present at the visit.

9 ADVERSE EVENTS

The Investigator is responsible for reporting all AEs that are observed or reported during the study, regardless of their relationship to study drug or their clinical significance.

Adverse event information will be collected beginning at enrollment (date of signed informed consent) and up to the end of the study. All ongoing AEs will be followed until ET or end of study (EOS), at a minimum, or until the Investigator and the Sponsor agree that further follow-up is not required. Requirements for SAE follow-up are detailed in [Section 9.3.3](#).

An AE is defined as any untoward medical occurrence in a patient enrolled into this study regardless of its causal relationship to study drug. Patients will be instructed to contact the Investigator at any time after randomization if any symptoms develop.

A TEAE is defined as any event not present before exposure to study drug or any event already present that worsens in either intensity or frequency after exposure to study drug.

9.1 Eliciting and Documenting Adverse Events

All AEs reported or observed during the study, including AEs resulting from concurrent illnesses, reactions to concurrent medications, or progression of disease states, will be recorded on the AE page in the eCRF and in the site source notes. The eCRFs used to document AEs are designed to help ensure this information is collected in a standard way. Information to be collected includes event term, date and time of onset, date and time of resolution, Investigator-specified assessment of severity and relationship to study drug, action taken with respect to study drug, seriousness, any required treatment or evaluations, and outcome. All AEs will be followed until the ET or EOS visit, at a minimum. The sites will be provided with completion guidelines for the eCRF, which will further guide them on how to record the data, including AEs. The MedDRA will be used to code all AEs.

Any medical condition that is present at the time that the patient signs informed consent but does not worsen should not be reported as an AE. However, if it worsens at any time during the study, it should be recorded as an AE. This includes any spontaneously reported worsening of depression, i.e., not based on the study rating scales.

In addition to observations of the patient, AEs identified from any study data (e.g., laboratory values, physical examination findings, ECG changes) or identified from review of other documents that are considered clinically significant will be documented on the AE page in the eCRF. Worsening of symptoms that are only detected on clinical effects rating scales will not be reported as AEs.

Adverse events will be assessed at each visit by direct questioning as well as elicited from physical examination by site staff. In addition, all sites in the study must ensure patients have a 24-hour telephone number to contact medical site staff for the duration of the study, in case of emergent AEs or SAEs.

If there is any doubt as to whether a clinical observation is an AE, the event should be reported.

9.2 Definitions of Adverse Event Severity and Relationship to Study Drug

9.2.1 Severity

The severity, or intensity, of an AE refers to the extent to which an AE affects the patient's daily activities. Adverse event severity will be evaluated using the criteria in [Table 7](#).

Table 7 Definitions of AE Severity Criteria

AE Severity	Definition
Mild	Mild; asymptomatic or mild symptoms; clinical or diagnostic observations only; intervention not indicated.
Moderate	Moderate; of sufficient severity to make the patient uncomfortable; minimal, local, or noninvasive intervention indicated.
Severe	Severe or medically significant, of sufficient severity to cause the patient severe discomfort; may cause cessation of treatment; treatment of event symptoms/intervention may be required.

Abbreviation: AE = adverse event.

Changes in the severity of an AE should be documented in the eCRF to allow an assessment to be performed of the duration of the event at each level of intensity.

9.2.2 Relationship to Study Drug and/or Study Procedure

The Investigator's assessment of an AE's relationship to study drug is part of the documentation process. All AEs, regardless of relationship, will be recorded in the eCRF. In addition, SAEs will be reported to regulatory authorities as required by local regulation ([Section 9.3.4](#)). In addition, the Investigator's assessment of an AE's relationship to study procedure should also be recorded.

The relationship or association of the study drug and/or study procedure in causing or contributing to the AE will be characterized using the classification and criteria presented in [Table 8](#).

Table 8 Guidelines for Determining the Relationship (if Any) Between Adverse Event and the Study Drug and/or Study Procedure

AE Relationship	Definition
Definite	This relationship suggests that a definite causal relationship exists between treatment administration and the AE, and that other conditions (concurrent illness, progression/expression of disease state, or concurrent medication reaction) do not appear to explain the event. The event reappears or worsens if the study drug is re-administered.
Probable	This relationship suggests that a reasonable temporal sequence of the event with treatment administration exists and, based upon the known pharmacological action of the treatment, known or previously reported adverse reactions to the treatment or class of treatment, or judgment based on the Investigator's clinical experience, the association of the event with the study drug seems likely. The event disappears or decreases on cessation of study drug.
Possible	This relationship suggests that the study drug caused or contributed to the AE, i.e., the event follows a reasonable temporal sequence from the time of treatment administration or follows a known response pattern to the study drug, but could also have been produced by other factors.
Unlikely Related	This relationship suggests an improbable (but not impossible) association between the study drug and the reported event.
Not Related	This relationship suggests no association between the study drug and the reported event.

Abbreviation: AE = adverse event.

9.3 Serious Adverse Events

9.3.1 Serious Adverse Event Criteria

An SAE is defined as any event that results in death, is immediately life-threatening, requires inpatient hospitalization or prolongation of existing hospitalization, results in persistent or significant disability/incapacity, or is a congenital anomaly. Important medical events that may not result in death, be life-threatening, or require hospitalization may be considered SAEs when, based on appropriate medical judgment, they may jeopardize the patient or may require medical or surgical intervention to prevent one of the outcomes listed in this definition. Examples of such medical events include allergic bronchospasm requiring intensive treatment in an emergency room or at home, blood dyscrasias or convulsions that do not result in inpatient hospitalization, or the development of drug dependency or drug abuse. A life-threatening event does not include an AE that, had it occurred in a more severe form, might have caused death.

Serious AEs must be reported ([Section 9.3.4](#)) and will be followed up until resolution. Serious AEs that occur after the final follow-up visit need not be reported unless the Investigator considers them related to study drug.

The Sponsor will provide a Sponsor causality statement for all SAEs.

9.3.2 Suspected Unexpected Serious Adverse Reactions

A suspected unexpected serious adverse reaction (SUSAR) is an SAE for which there is a reasonable possibility that the drug caused the event, and this SAE has not been previously identified as an expected/listed adverse event. A list of expected adverse events (if applicable) is provided in the current version of the IB and is considered the Reference Safety Information (RSI) for the study. Generally, the indication for which a product is intended would not be on the list of expected adverse reactions, but if it did occur, would not be considered “unexpected” for SUSAR reporting. As an example, a flare-up of symptoms consistent with the underlying disease under treatment that required hospitalization would constitute a serious adverse reaction; however, the event would not be considered unexpected. An exception would be if the reporter believed that study drug worsened the underlying condition.

9.3.3 Serious Adverse Event Follow-up

Appropriate remedial measures should be taken by the Investigator using his/her best medical judgment to treat the SAE. These measures and the patient’s response to these measures should be recorded. All SAEs regardless of relationship to study drug will be followed by the Investigator until resolution. Clinical, laboratory, and diagnostic measures should be employed by the Investigator as needed to adequately determine the etiology of the event.

9.3.4 Serious Adverse Event Reporting

9.3.4.1 Reporting Requirements

Any AE that meets SAE criteria ([Section 9.3.1](#)) must be reported to the Sponsor and/or designee immediately (i.e., within 24 hours) after the site personnel first learn about the event using the SAE Report Form provided for the study. Regardless of causality, all SAEs that occur during the study (from the time the patient signs the ICF to the ET/EOS visit) must be reported to the Sponsor and recorded on the AE page of the patient’s eCRF and in the patient’s source documentation/medical file. Related SAE(s) that commence after the ET/EOS visit should be recorded in the patient’s medical file and reported to the Sponsor but will not be added to the eCRF.

The initial report should include at least the following information:

- Study number
- Patient’s identification number
- Description of the event

- Date and time of onset of the event
- Seriousness criteria
- Causality assessment to study drug

If follow-up is obtained or requested by the Sponsor and/or designee, the additional information should be emailed on an SAE Report Form to the Sponsor in a timely manner according to the procedures and timelines outlined above. Copies of discharge summaries, consultant reports, autopsy reports, and any other relevant documents may also be requested.

The Investigator will be responsible for reporting all SAEs to the Institutional Review Board (IRB) or Ethics Committee (EC). The Sponsor will be responsible for reporting to the regulatory authorities and Central Ethics Committees, as per local requirements.

9.3.4.2 *SAE Contact Information*

Serious adverse event contact information is provided below.

[REDACTED]

[REDACTED]

North America

[REDACTED]

[REDACTED]

EMEA/APAC

[REDACTED]

[REDACTED]

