3 STUDY OBJECTIVES

Primary Objective:

- To evaluate the safety and tolerability of WVE-003 in patients with HD

Secondary Objectives:

- To characterize the PK of WVE-003 in plasma
- To characterize the concentration of WVE-003 in CSF

Exploratory Objectives:

- To evaluate the PD effect of WVE-003 on the levels of mHTT protein in CSF
- To evaluate the effect of WVE-003 on clinical measures of disease including the Unified Huntington's Disease Rating Scale (UHDRS) and Short Problem Behaviors Assessment (PBA-s)
- To evaluate the PD effects of WVE-003 on relevant biomarkers in CSF, plasma, and peripheral blood mononuclear cells (PBMCs) (e.g., levels of wtHTT protein, total huntingtin [tHTT] protein in CSF, and neurofilament light [NfL] in CSF and plasma)
- To evaluate changes from baseline in magnetic resonance imaging (MRI) of the brain

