Within 1 week prior to performing any lumbar puncture, a blood sample will be tested locally for platelet count and prothrombin time to confirm that it is safe to proceed with the lumbar puncture. Other predose assessments may also be performed up to 1 week prior to dosing as specifically listed in [Table 3](#) including UHDRS, PBA-s, and weight.

The Period 2 MAD cohorts will be conducted in a sequential manner. Subsequent multiple-dose cohorts will not initiate until the criteria for dose escalation are met ([Section 4.4.1.3](#)).

Immediately after study drug administration in any cohort, all patients should be ambulatory and active for approximately 30 minutes postdose on all dosing days. The Investigator should note any weakness or fatigue during this period. Formal physical examinations targeting the neurological system will be performed postdose at the time points specified in [Table 3](#).

Patients will attend clinic visits Q4W for assessments of safety, PK, and PD. Patients in P2C1 will receive doses on Week 0, Week 8, and Week 16. Pending DEC/SMC recommendation, subsequent cohorts may receive doses Q8W or less frequently (e.g., on Week 0 and Week 12).

4.1.4.4 *Period 2 Follow-up*

All patients are required to complete follow-up assessments, including evaluations of safety, PD, PK, clinical effects, and MRI. Patients will be followed up for a minimum of 12 weeks after the last dose. Any postdose SAEs will be monitored until resolution.

4.1.5 *Early Termination Visit*

If a patient withdraws from the study early, the patient should complete an early termination visit. Refer to [Section 5.3](#) for information on early withdrawal from study drug or from the study.

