5.3.1 Withdrawal of Patients From the Study

Patients must be withdrawn from the study for any of the following:

- Patient's withdrawal of consent
- At the discretion of the Investigator for medical reasons
- At the discretion of the Investigator or Sponsor for noncompliance
- Significant protocol deviation
- Termination of the study by the Sponsor (see [Section 14.4](#) for additional details)

In addition, the Sponsor may withdraw a patient from the study at their discretion and for any reason.

Any patient for whom consent to participate in the study is withdrawn will be removed from further treatment and study observation immediately upon the date of request. It should be encouraged that these patients complete the early termination study procedures ([Section 4.1.5](#)) and observations at the time of withdrawal. All information, including the reason for withdrawal from the study, must be recorded in the eCRF and source documentation.

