11.3.4 Analysis of Safety Data

The summary of safety results will be presented by dose group. All safety analyses will be performed on the safety population using the following common rules:

- The baseline value is defined generally as the last available value before randomization.
- Adverse event observation periods are defined as follows:
 - Pretreatment AEs are AEs that developed or worsened prior to the first dose of study drug.

- On-treatment adverse events are AEs that developed or worsened from the first dose of study drug to study completion/discontinuation. Summaries of TEAEs will include all on-treatment AEs.
- For quantitative safety parameters based on central laboratory/reading measurement, descriptive statistics will be used to summarize results and change from baseline values by visit and treatment group.

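### In patients who leave the study within 12 weeks of a dose, a related SAE after the early-termination visit is kept out of the eCRF and the on-treatment window, while the same event in a completer is counted

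*Combined protocol and SAP*

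**What the plan says.** The primary objective is a safety one: "To evaluate the safety and tolerability of WVE-003 in patients with HD" (Section 3).

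**Collection.** Section 9.3.4.1 requires all SAEs, whatever their cause, to be reported and entered in the eCRF "from the time the patient signs the ICF to the ET/EOS visit". A related SAE that begins later goes to the patient's "medical file and reported to the Sponsor but will not be added to the eCRF". Under Section 9.3.1, an SAE after the final follow-up visit has to be reported only if the Investigator judges it related.

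**Analysis.** Section 11.3.4 states: "On-treatment adverse events are AEs that developed or worsened from the first dose of study drug to study completion/discontinuation". It adds: "Summaries of TEAEs will include all on-treatment AEs". Section 9 is open-ended: "A TEAE is defined as any event not present before exposure to study drug", or one that worsens after exposure, with no closing date.

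**Follow-up.** Section 4.1.4.4 says for Period 2: "Patients will be followed up for a minimum of 12 weeks after the last dose". Section 4.1.3.2 sets the same 12-week minimum for Period 1. Section 4.1.5 ties the ET visit to early withdrawal from the study and sets no minimum time since the last dose. Under Section 5.3.1, a patient who withdraws consent "will be removed from further treatment and study observation immediately upon the date of request". That section also requires withdrawal for medical reasons, noncompliance or a significant protocol deviation, and lets the Sponsor withdraw a patient for any reason.

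**The concern.** The cut-off for entering a related SAE is a visit, not a time since dosing. For a completer the final visit falls at the end of the planned follow-up, so the rule does little harm. For someone who leaves the study, the ET visit can come days or weeks after a dose, and the same rule then closes the record early. Two patients with the same related SAE at the same interval after the same dose can be treated differently only because one of them had already left.

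What is at stake is whether the safety tables for the primary objective are complete in small dose groups, where a single related SAE changes the reading of a cohort. The Sponsor could hold a report of a related SAE that its own summaries do not show.

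**Working it through.** The plan gives no figure to reproduce. The check sets the collection rule against the analysis rule and then sizes one omitted event.

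**1. A completer in P2C1.** Doses are at Weeks 0, 8 and 16 (Section 4.1.4.3), and the final visit is at Week 28 (Table 3). 28 − 16 = 12 weeks, which equals the stated minimum follow-up.

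**2. An early leaver.** As an illustration, take an ET visit 1 week after a dose and a new related SAE 3 weeks after that dose. The event is inside the 12-week period (3 < 12) but after the ET visit (3 > 1).

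| Rule | Completer, related SAE at 3 weeks | Early leaver, related SAE at 3 weeks |
|---|---|---|
| Reported to the Sponsor (9.3.1, 9.3.4.1) | Yes | Yes |
| Entered in the eCRF (9.3.4.1) | Yes | No |
| On-treatment AE (11.3.4) | Yes | No |
| TEAE by definition (9) | Yes | Yes |

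The last two rows disagree for the early leaver, so Sections 9 and 11.3.4 are not reconciled.

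**3. There are two barriers.** Removing the eCRF exclusion alone would leave the event outside the on-treatment window. Extending the window alone would leave no eCRF record to tabulate. No section says that the Sponsor's later SAE reports are merged into the tables.

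**4. Size of one omitted event.** P1C3 is planned at n = 12 with 2:1 allocation (Section 2.3), so active n = 12 × 2/3 = 8. Exact (Clopper-Pearson) 95% intervals are:

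- With the event: 1/8 = 12.5%, interval 0.3% to 52.7%.
- Without it: 0/8 = 0%, upper limit 1 − 0.025^(1/8) = 36.9%.

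P2C1 is planned at about 24 patients, but its allocation ratio is not stated. Assuming a ratio between 1:1 and 3:1:

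- 1:1: 12 active, 1/12 = 8.3%.
- 2:1: 16 active, 1/16 = 6.25%.
- 3:1: 18 active, 1/18 = 5.6%.

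**5. How often.** The expected number of omitted events is the number of patients whose ET visit falls within 12 weeks of the last dose, times the chance of a new related SAE between that visit and week 12. The documents give neither figure, so only the per-event effect can be stated.

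**The case against.** The strongest reply is that the affected group is narrow and the gap is one of tabulation only. Much of this stands.

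- **Stopping drug is not leaving the study.** Section 5.3.2 urges patients who stop treatment to stay for all procedures and allows longer follow-up after an AE. Section 4.4.3.3 keeps patients who meet individual stopping criteria under safety follow-up. SAEs that start before the ET visit are followed to resolution (Section 9.3.3). Many patients who tolerate treatment poorly therefore stay inside the window.
- **Oversight is intact.** The related SAE still reaches the Sponsor, and expedited reporting does not depend on eCRF entry.
- **Omission from every output is not established.** Section 11.3.4 says the summaries include on-treatment events without saying only those. Section 11.3.4.1 promises listings of all SAEs without restricting the source to the eCRF. Section 11.3.6 refers to an SAP still to be finalised, which might deal with reconciliation, although nothing in the available text does so.

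A reader might go further and infer that the rule costs an early leaver most of the follow-up, for instance 11 of 12 weeks (92%) after an ET visit at week 1. That loss comes from the patient leaving and visits ending. Changing the eCRF sentence restores no visits; it recovers only related SAEs that someone reports.

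A reader might also infer that the active-arm SAE rate is biased downward against placebo. That would need more early leaving on active treatment, or more related events after leaving, and the documents show neither.

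The reply does not remove the unequal treatment of the same event, the conflict between Sections 9 and 11.3.4, or the lack of any stated route by which these reports enter the summaries.

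**Conclusion.** The point holds in a limited form. For patients who leave the study with an ET visit less than 12 weeks after their last dose, the plan as written leaves a later related SAE within the protocol's own follow-up period out of the eCRF and outside the on-treatment set used for the primary-objective summaries. A completer's identical event is counted.

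Each omitted event is worth 12.5 percentage points among the 8 active P1C3 patients, and between 5.6 and 8.3 points in P2C1 under assumed ratios of 3:1 to 1:1. The number of such events cannot be estimated and may be zero. The documents do not support a claim that safety reporting fails, that the event is missing from all outputs, or that the comparison with placebo is biased in a known direction. This is an inexpensive improvement to make; it does not undermine the trial.

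**What to change.** 1. **Section 9.3.4.1.** Enter in the eCRF any related SAE that starts up to the later of the ET/EOS visit or 12 weeks after the last dose, subject to the patient's consent status. If eCRF entry is impractical, reconcile these events into the analysis data from the Sponsor's SAE reports. The present rule can stay for later events.
2. **Section 11.3.4.** Reconcile the on-treatment window with the Section 9 definition of a TEAE, and state the closing date explicitly.
3. **Presentation.** Show related SAEs that start after the ET visit by dose group in a separately labelled table, with a total that includes them. They should not be folded unmarked into the main table. Before the ET visit all SAEs are actively sought whatever their cause; afterwards only related ones are reported, and passively. Mixing the two would blur what the rates mean.
4. **Listings.** State in Section 11.3.4.1 whether the SAE listings draw on events held outside the eCRF.

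The cost is protocol and SAP wording, one extra table, and keeping an early leaver's record open to 12 weeks after the last dose. The Sponsor already receives these reports, so no visits or procedures are added and clinical management does not change. Passive reporting will still miss events that nobody reports, and the table should carry a footnote saying so.
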